14.3 Shipping and Handling

14.31 Correlative studies will be performed at Hormel Institute, University of Minnesota, by [REDACTED] Samples can be shipped Monday-

Thursday. Samples that come in on Friday will be refrigerated and shipped on the following Monday. Label the individual samples with the study number MC1483 and the unique study identification number for the patient.

Please ship to the address below.

[REDACTED]

Contact information is below.

[REDACTED]

14.32 FLT3 analysis gene sequencing will be performed at the Mayo Clinic in Rochester, MN, per standard testing.

14.33 Handling Specimens

After receipt by the analytical laboratory, samples will be stored at -20 °C or less until analysis.

15.0 Drug Information

15.1 Midostaurin (PKC412, CGP41251)

15.11 **Background:** Midostaurin inhibits several protein kinase C (PKC) isoforms of the tyrosine kinase of the vascular endothelial growth factor receptor (VEGFR) and, most importantly, of the class III tyrosine protein kinases FLT3 (fms-like tyrosine kinase-3) and KIT, which are involved in hematopoiesis as well as playing a key role in certain hematopoietic disorders. Midostaurin binds to the catalytic domain of these kinases and inhibits the mitogenic signaling of the respective growth factors in cells and results in growth arrest.

Importantly, midostaurin has been found to revert the P-glycoprotein (Pgp) mediated MDR (multidrug resistance) phenotype by inhibiting the function of Pgp. Studies which analyzed the sensitivity of Pgp expressing and non-expressing AML blast cells with either FLT3-ITD (internal tandem duplication) mutations or FLT3 wild-type (WT) status towards midostaurin, indicated significant pro-apoptotic activity of midostaurin against both mutated and non-FLT3-mutated blast cells with Pgp expression.

Efficacy of midostaurin has also been shown for myeloproliferative disorders (MPD) induced by ZNF198-FGFR1 or by FIP1L1-PDGFR α .

- 15.12 **Formulation:** Midostaurin is available as 25 mg soft gelatin capsules, a 25 mg/mL oral solution for pediatric patients, and a 50 mg/5 mL IV solution for infusion (limited to use in the absolute BAV study CPKC412A2120)

The capsule filling solution contains the following excipients, in addition to the drug substance: all-rac- α -Tocopherol / vitamin E, corn oil-mono-di-triglycerides, dehydrated alcohol, polyethylene glycol 400, polyoxyl-40-hydrogenated castor oil. The capsule shell contains gelatin (porcine), glycerol, iron oxide red, iron oxide yellow, and titanium dioxide. The capsules are printed and contain traces of the following excipients: carminic acid E120, aluminum chloride hexahydrate / aluminum chloride, sodium hydroxide, hypromellose, propylene glycol, and isopropyl alcohol.

The 25 mg/mL oral solution contains all-rac- α -tocopherol / vitamin E, corn oil-mono-di-triglycerides, dehydrated alcohol, polyethylene glycol 400, polyoxyl 40 hydrogenated castor oil.

The IV solution for infusion contains propylene glycol 300, polysorbate 80, and dehydrated alcohol.

- 15.13 **Preparation and storage:** The soft gelatin capsules are packaged in blister packs which are to be stored below 25°C. The oral solution is provided in a 50 mL amber glass bottle and should be stored at 2-8°C before first use. The IV solution for infusion should be stored at 2-8°C, protected from light.
NOTE - The medicine must be disposed properly. After use, remaining capsules, closed oral solution bottles, and the corresponding dispensing system should be returned to the clinical site. Spills should be removed immediately by the use of paper tissue and disposed in a trash bin. The product should not be disposed in a sink or toilet. Contact of the product with the skin should be avoided.
- 15.14 **Administration:** Midostaurin should be administered orally, twice daily at the same time every day and together with food.

Capsules should be swallowed whole with a glass of water, and must not be chewed or crushed. Remove from the blister pack just prior to administration.

Midostaurin 25 mg/mL oral solution should be allowed to equilibrate to room temperature for approximately 1 hour until the solution is clear. Dose is withdrawn using a 1 mL or 4 mL oral syringe and diluted in water prior to administration. Dose must be taken immediately after dilution.

15.15 Pharmacokinetic information:

a) Absorption – rapid oral absorption of midostaurin with T_{max} of 1-3 hours. C_{max} and AUC of midostaurin increase in an apparent doseproportional manner after administration of single doses up to 50mg and in a less than proportional manner thereafter. Upon daily oral dosing, midostaurin concentrations accumulated in a time-linear manner in the first 3-6 days. Thereafter, the PK becomes time-dependent; the plasma concentrations of midostaurin decreased substantially between Days 6-14, and reached a new plateau after 2-3 weeks of daily dosing. The AUC_{inf} of midostaurin increased by 22% and by 59% with standard meal and high fat meal respectively. The C_{max} was decreased by 20% and 27%, respectively. Median T_{max} of midostaurin was delayed with administration of a meal compared to the fasted condition by 2.5 to 3h. The recommendation is to administer midostaurin with food.

b) Distribution – Midostaurin was observed to be widely distributed in humans with a high tissue distribution of $V_z/F= 99$ L. Midostaurin and its metabolites were distributed mainly in plasma rather than red blood cells. [¹⁴C] midostaurin was highly bound to human plasma proteins (99.2%), which was also observed in patients. The binding was independent of concentration over the concentration range of 100 – 5000 ng/mL, and was unaffected by high concentrations of α -acid glycoprotein.

c) Metabolism – Midostaurin is predominantly metabolized by CYP3A4 into two major active circulating metabolites, CGP62221 (via O-demethylation) and CGP52421 (via hydroxylation) in humans. The concentration of CGP52421 increased gradually with time and appeared to reach a steady state after 28 days of a multiple dosing regimen. It is possible that auto-induction, protein binding competition and displacement, and/or a combination of both play a role in the pharmacokinetics of midostaurin.

d) Excretion – Elimination of midostaurin from plasma was slow with an apparent terminal half-life of about 17 hours (range 5-31 hours). The apparent terminal half-life of CGP62221 was estimated as 39 hours. The metabolite CGP52421 accumulated in plasma over treatment cycles and its apparent terminal half-life was estimated as >1 month. Fecal excretion is the major pathway for elimination of midostaurin, CGP62221, and CGP52421. Urinary excretion plays a minor role.

- 15.16 **Potential Drug Interactions:** Some preclinical observations suggest that midostaurin may enhance the effect of irradiation, but the potential clinical significance in terms of risk-benefit of this is currently unknown. The effect is more pronounced in p53+ than in p53- cells.

Co-administration of midostaurin with the potent CYP3A4 inhibitor ketoconazole, resulted in a 10-fold increased exposure of midostaurin. However, data from studies evaluating the co-administration of strong CYP3A4 inhibitors with midostaurin indicate the potential to increase exposure of midostaurin, with little clinical relevance. Nevertheless, co-administration of a strong CYP3A4 inhibitor with midostaurin should be handled with caution. CYP3A4 strong inhibitors include: clarithromycin, telithromycin, troleandomycin, indinavir, lopinavir, nelfinavir, ritonavir, saquinavir, tipranavir, itraconazole, ketoconazole, posaconazole, voriconazole, boceprevir, telaprevir, cobicistat, conivaptan, nefazodone.

Caution should be exercised for patients receiving moderate CYP3A4 inhibitors. A list of these agents is found at:

<http://medicine.iupui.edu/clinpharm/ddis/main-table>

Co-administration of midostaurin with the potent CYP3A4 inducer, rifampicin, decreased the C_{max} and AUC of midostaurin by 73% and 94%, respectively. To avoid sub-therapeutic exposure to midostaurin, moderate or strong CYP3A4 inducers should not be co-administered. Strong CYP3A4 inducers include: avasimibe, carbamazepine, mitotane, phenobarbital, phenytoin, rifabutin, rifampin (rifampicin), and St. John's wort. Moderate CYP3A4 inducers include: bosentan, efavirenz, etravirine, genistein, modafinil, nafcillin, ritonavir, talviraline, thioridazine, and tipranavir.

- 15.17 **Known potential toxicities:** Aggressive Systemic Mastocytosis (ASM), and Acute Myeloid Leukemia (AML)

Very Common (>10%): leukopenia, lymphopenia, febrile neutropenia (AML), petechiae, sinus tachycardia, anorectal discomfort, constipation, diarrhea, hemorrhoids, stomatitis, nausea, vomiting, fatigue, peripheral edema, pyrexia, hypersensitivity (AML), device related infection, URTI (ASM), UTI, APTT prolonged, increased ALT, increased AST, increased amylase, increased lipase, decreased hemoglobin, decreased neutrophil count, decreased absolute neutrophils, decreased absolute lymphocytes, hyperglycemia, increased glucose, hypokalemia, hyponatremia, increased total bilirubin, hyperuricemia, back pain, arthralgia, headache, dizziness, insomnia, cough, dyspnea, epistaxis, pleural effusion (ASM), laryngeal pain, hyperhidrosis, exfoliative dermatitis, hypertension,

hypotension (AML)

Common (> 1- 10%): febrile neutropenia (ASM), pericardial effusion, eyelid edema, vertigo, abdominal discomfort, abdominal distension, dyspepsia, GI hemorrhage, asthenia, chills, edema, catheter related thrombosis, hypersensitivity (ASM), bronchitis, erysipelas, cystitis, herpes zoster, oral herpes, pneumonia, sepsis, sinusitis, URTI (AML), hypercalcemia, increased weight, confusion, fall, bone pain, pain in extremities, neck pain, syncope, tremor, disturbance in attention, ARDS, pleural effusion (AML), oropharyngeal pain, nasopharyngitis, keratitis, dry skin, hematoma, hypotension (ASM)

Uncommon ($\geq 0.1 - 1\%$): anaphylactic shock, neutropenic sepsis

- 15.18 **Drug procurement:** Midostaurin capsules will be provided free of charge to study subjects by Novartis.
- 15.19 Nursing Guidelines
- 15.191 Patients should be instructed to take medication at the same time every day, twice daily with food. Capsules must be swallowed whole with a glass of water and cannot be chewed or crushed. Oral solution is available for pediatric patients—follow separate preparation instruction in section 15.14. Medicine must be properly disposed of. Do not pour down a sink or toilet. Wipe up spills immediately. Avoid skin contact.
- 15.192 Assess patient's concomitant medications, including OTC and herbal products. Midostaurin has interactions with drugs that are metabolized via CYP3A4 and caution should be exercised for patients who are on these agents. For more details refer to section 15.16 of the protocol.
- 15.193 Gastrointestinal side effects are common, including nausea, vomiting, and diarrhea. Treat symptomatically and monitor for effectiveness. Patients should be premedicated for the prevention of nausea and vomiting.
- 15.194 Monitor creatinine and renal function as renal impairment/failure has been seen.
- 15.195 Instruct patients to report any signs/symptoms of CHF/LVEF dysfunction, including chest pain, SOB, and edema.
- 15.196 Monitor CBC w/diff as cytopenias can be seen. Instruct patients to report any signs/symptoms of infection and/or any unusual bruising/bleeding to the study team.
- 15.197 Monitor glucose levels per protocol as hyperglycemia has been seen. Diabetics may need additional monitoring.

15.198 Back pain and arthralgia's have been seen. Treat symptomatically and monitor for effectiveness.

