4.0 Test Schedule

All routine assessments must be performed within ± 7 days of the day indicated on the Visit Schedule.

Tests and procedures	Pre-Treatment	Active Treatment					
	≤ 7 days prior to registration*	Cycle 1, Day 1	Cycle 1, Day 8	Cycle 1 Day 21	Cycles 2 and above, Day 1	Cycles 2 and above, Day 8 ⁷	Early Discontinuation or End of Treatment
History and exam, weight, vitals, PS	X	X			X	X	X
Height	X						
Adverse event assessment	X	X			X		X
BM testing ²	X				X ²		X
Biomarkers FLT3 Mutation by PCR	X						X
Pregnancy Test	X						
Hematology group(CBC) Hgb, , PLT, WBC with diff. ¹	X	X ¹	X	X	X ¹	X	X
Serum Chemistry (magnesium, potassium, phosphorus, total bilirubin, direct bilirubin ⁵ , alkaline phosphatase, AST, ALT, creatinine)	X	X	X	X	X	X	X
Serum Chemistry (Serum Amylase & Lipase)	X	X			X		X
MUGA/Echo	X						
LDH	X						
Urine analysis (proteinuria, hematuria) ^R	X						
ECG (QTcF results preferred) ^{R 3}	X		X			X ³	X
Patient Medication Diary (Appendix III ⁴)			X		X	X	
Research Correlatives ^{R, 6}	X		X		X ⁶		

* Labs done on the same day of consent but prior to consenting do not need to be repeated.

1. CBC will be done weekly for cycle 1-4. After cycle 4, to be performed Day 1 and Day 8.
2. Bone marrow (BM) sampling will be done upon screening, and day 1 of cycle 3, 5, 9 and then as clinically needed. Recent bone marrow within 21 days (even prior to consenting) will be acceptable and FLT3 PCR could be done on peripheral blood if blasts >10%. Outside FLT3

testing at bone marrow biopsy will be allowed and used if done.

3. ECGs will be performed locally at screening, Day 8 (prior to dosing) of each cycle, and when there's any dose change due to QTc prolongation or re-initiation after a dose interruption. When a dose change occurs due to QTc prolongation or upon re-starting midostaurin, an ECG must be obtained at 7 days afterwards. QTcF results are preferred, however all reporting methods will be accepted.
 4. The diary must begin the day the patient starts taking midostaurin and must be completed per protocol and returned to the treating institution OR compliance must be documented in the medical record by any member of the care team. Patients will be asked to return all unused medication at each visit.
 5. Get direct bilirubin if total bilirubin > upper normal limit.
 6. Correlatives for blood and bone marrow. See section 14.

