Accrual will be temporarily suspended to this study if at any time we observe events considered at least possibly related to study treatment (i.e. an adverse event with attribute specified as "possible," "probable," or "definite") that satisfy one of the following:

- if 4 or more patients in the first 12 treated patients experience a grade 4 or higher non-hematologic adverse event at least possibly related to treatment excluding infections and hypophosphatemia, hypocalcemia, hypo- or hyperkalemia, hyperuricemia as these abnormal lab results tend to resolve quickly (≤ 7 days) without affecting or jeopardizing patient safety.
- if after the first 12 patients have been treated, 30% of all patients experience a grade 4 or higher non-hematologic adverse event at least possibly related to treatment excluding infections and hypophosphatemia, hypocalcemia, hypo- or hyperkalemia,

hyperuricemia as these abnormal lab results tend to resolve quickly (≤ 7 days) without affecting or jeopardizing patient safety.

We note that we will review grade 4 and 5 adverse events deemed “unrelated” or “unlikely to be related”, to verify their attribution and to monitor the emergence of a previously unrecognized treatment-related adverse event.

16.5 Results Reporting on ClinicalTrials.gov: At study activation, this study will have been registered within the “ClinicalTrials.gov” website. The Primary and Secondary Endpoints along with other required information for this study will be reported on ClinicalTrials.gov. For purposes of timing of the Results Reporting, the initial estimated completion date for the Primary Endpoint of this study is 2.5 years after the study opens to accrual. The definition of “Primary Endpoint Completion Date” (PECD) for this study is at the time the last patient registered has been followed for at least 6 months.

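### The midostaurin guidance relies on protocol glucose monitoring, but the test schedule contains no glucose or sodium test, so detection of two expected toxicities is left to routine care

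*Combined protocol and SAP*

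**What the plan says.** The nursing guidelines for midostaurin (15.197) say: "Monitor glucose levels per protocol as hyperglycemia has been seen". They add that diabetic patients may need further monitoring.

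The main chemistry row of section 4.0 covers "magnesium, potassium, phosphorus, total bilirubin, direct bilirubin" and "alkaline phosphatase, AST, ALT, creatinine". It is drawn at screening, on days 1, 8 and 21 of cycle 1, on days 1 and 8 of later cycles, and at the end of treatment. A second chemistry row covers amylase and lipase. LDH is measured before treatment only, and so is the urine test, which is "Urine analysis (proteinuria, hematuria").

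The very common (above 10%) midostaurin toxicities in 15.17 include "hyperglycemia, increased glucose, hypokalemia, hyponatremia, increased total bilirubin, hyperuricemia". The above-10% list for decitabine in 15.27 also has hyperglycemia and hyponatremia.

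The stopping rule in 16.42 counts related non-hematologic events of grade 4 or higher, "excluding infections and hypophosphatemia, hypocalcemia, hypo- or hyperkalemia, hyperuricemia as these abnormal lab results tend to resolve quickly". Hyperglycemia and hyponatremia are not among the exclusions. Section 16.325 tabulates each patient's maximum grade for each type of event.

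**The concern.** The instruction in 15.197 refers to monitoring that the protocol does not contain. A nurse following it would reasonably assume that the scheduled panel covers glucose.

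Hyperglycemia and hyponatremia are found by measurement. Without a scheduled test, finding them depends on which patients have other chemistry done, and when. No baseline value is required either, so a later abnormal value may have nothing to be compared with.

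Three parts of the plan depend on this:

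- **Safety goal.** Goal 2.24 (safety by CTCAE) and the 16.325 tables would mix standardised and incidental ascertainment without saying so.
- **Stopping rule.** A related grade 4 glucose or sodium event should count under 16.42, but it can count only if someone measures it.
- **Other sections.** Section 3.24 gives uncontrolled diabetes as an example of an excluding condition, and 8.2 links midostaurin actions to grade 3 and 4 non-hematologic toxicity. Applying either to glucose presupposes a measurement that section 4.0 does not require.

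**Working it through.** The plan states no figure on this point, so there is none to reproduce. The check is a comparison of sections, followed by two illustrations.

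**1. Is glucose required anywhere else?** The eligibility laboratory values (3.15) are amylase, lipase, bilirubin, alkaline phosphatase, AST, ALT and creatinine. The solicited events (10.51) are QTc prolongation, bilirubin, ALT, AST, lipase and rash. Neither list has glucose or sodium. Of the laboratory tests named in the midostaurin nursing guidelines, creatinine (15.194) and the blood count (15.196) are scheduled in 4.0. Glucose is the only one that is not.

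**2. Which expected laboratory toxicities have no scheduled test?** Taking the above-10% lists of both drugs:

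| Laboratory toxicity | Midostaurin 15.17 | Decitabine 15.27 | Scheduled in 4.0 |
|---|---|---|---|
| Blood count decreases (leukopenia, neutropenia, anemia) | >10% | >10% | yes |
| Hypokalemia | >10% | >10% | yes |
| Raised bilirubin | >10% | >10% | yes |
| Hyperglycemia | >10% | >10% | **no** |
| Hyponatremia | >10% | >10% | **no** |
| Hyperuricemia | >10% | 1-10% | no |

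Glucose and sodium are the two gaps common to both drugs.

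**3. Effect on a reported rate (illustration).** Let p be the true rate of an event and s the probability that a case is detected. The documents do not give s, so it is an assumption. The observed rate is s × p, and the chance of at least one observed case in 24 patients is 1 − (1 − s·p)^24.

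| p | s | Observed rate | Chance of at least 1 in 24 |
|---|---|---|---|
| 10% | 1 | 10% | 0.92 |
| 10% | 0.75 | 7.5% | 0.85 |
| 10% | 0.5 | 5% | 0.71 |
| 10% | 0.25 | 2.5% | 0.46 |
| 20% | 1 | 20% | 0.995 |
| 20% | 0.5 | 10% | 0.92 |
| 20% | 0.25 | 5% | 0.71 |

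Missed detection can only lower a rate. With s = 1 there is no bias.

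**4. Effect on the stopping rule (illustration).** Accrual is suspended if 4 or more of the first 12 patients have a qualifying event. Let b be the rate of other qualifying events and g an independent rate of related grade 4 glucose or sodium events, both assumed. The rate the rule sees is q = 1 − (1 − b)(1 − g·s), and the trigger probability is P(X ≥ 4) for X binomial(12, q).

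| b | g | s | q | Trigger probability |
|---|---|---|---|---|
| 0.20 | 0.05 | 1 | 0.24 | 0.320 |
| 0.20 | 0.05 | 0.5 | 0.22 | 0.261 |
| 0.20 | 0.05 | 0 | 0.20 | 0.205 |
| 0.25 | 0.05 | 1 | 0.2875 | 0.469 |
| 0.25 | 0.05 | 0 | 0.25 | 0.351 |

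Under these assumptions, undetected events lower the chance of a suspension by up to about 0.12 (0.320 − 0.205 = 0.115; 0.469 − 0.351 = 0.118).

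**The case against.** The strongest reply is that routine care probably measures these analytes. Section 9.3 requires full supportive care, adverse events are assessed on day 1 of every cycle and at the end of treatment, and 10.52 requires submission of related grade 2 events and all grade 3 and 4 events, however they were found. This stands in part. It is why the rates may be too low; a reader might infer that they will be, but the documents do not show that. They do not say which routine chemistries are run. Section 10.52 governs what is submitted once known, not what is looked for. Section 7.11 also allows decitabine on days 2-5 to be given by a local physician outside the center, so incidental testing may differ between patients.

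A second reply is that 15.19 is general drug-information text. It discusses an oral solution for pediatric patients in a trial for ages 60 and over. The reference to the protocol may then be a leftover phrase, and rewording 15.197 would remove the contradiction. That is true of the wording, but it would leave detection as it is.

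A third reply is that a listed toxicity need not have a scheduled test: prolonged APTT (15.17) and hypoalbuminemia (15.27) are above 10% and also unscheduled. This too is fair, and no section promises a scheduled sodium test. The case for sodium is therefore weaker than for glucose. It rests on the above-10% listing for both drugs and on the stopping rule, not on a broken reference.

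**Conclusion.** The point holds as an internal inconsistency with a possible downward bias in secondary safety results. Section 15.197 relies on a glucose test that section 4.0 does not schedule, and sodium is unscheduled too, although both drugs list the corresponding toxicities at above 10% and the stopping rule counts them. The bias is of unknown size and is zero if routine care always measures both. The figures in the two illustrations rest on assumed detection probabilities and event rates.

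Some stronger readings are not supported:

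- **Calcium.** It is also unscheduled, but hypercalcemia is only in the 1-10% list for midostaurin, and hypocalcemia is in neither drug's list.
- **Hypocalcemia and hyperuricemia in 16.42.** The rule excludes both, so missing them cannot weaken it.
- **A count of lost events.** One might take 0.10 × 24 = 2.4 patients per event as the loss. The frequency class carries no grade and covers mastocytosis as well as AML. Grade 1 events and unrelated grade 2 events outside 10.51 are not submitted even when measured. The 16.325 denominator is all eligible treated patients, not necessarily 24.

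The CR/CRi endpoint, the decision rule and the sample size are not affected.

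**What to change.** Reconcile 15.197 with 4.0. The most direct way is to add glucose and sodium to the existing Serum Chemistry row, on the days already scheduled and including screening. Uric acid could be added as an option, since hyperuricemia is listed at above 10% for midostaurin. The cost is a small laboratory charge on blood already drawn, with no new visit or procedure.

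In 16.325, report all events however they were found, and state which laboratory events were ascertained on schedule and which incidentally. The tables should not be restricted to scheduled panels: that would discard real grade 3 and 4 events that 10.522 requires to be submitted and 16.325 tabulates. Adding the tests will not recover grade 1 events, because 10.52 does not collect them outside the solicited list, and the report should say so.
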